6.4 Immunogenicity PP (IPP) Set

The IPP set will consist of the subset of subjects who participated in the immunogenicity portion of the study, who had a Day 21 immunogenicity sample collection; who had no major deviations related to subject eligibility, the ability to develop a valid immune response, prohibited medication use, or the immunogenicity analyses; and who received the vaccine or placebo. Subjects who received the wrong treatment, but for whom the treatment received can be unequivocally confirmed, will be analyzed as treated, provided they have no other deviations that compromise their data.

The analyses of all immunogenicity endpoints will be performed using the IPP set.

6.5 Protocol deviations/violations and exclusions from analysis sets

A protocol deviation is any change, divergence, or departure from the study design or procedures of a study protocol. Major and minor protocol deviations will be identified and documented during a blinded data review prior to database lock. Subjects will be excluded from analyses if the deviation is considered to impact the analyses.

Prematurely terminating study participation for reasons such as withdrawal of consent or occurrence of adverse events (including death) is not considered as a protocol deviation. The missing assessments that should have otherwise been collected for that subject later in the study are also not considered as a protocol deviation.

Protocol deviations will be reviewed by Medicago (or its designee) to identify any non-compliances likely to have a significant effect on the safety and rights of a subject or the reliability and robustness of the data generated. These deviations will be included in the clinical study report.

7 STATISTICAL CONSIDERATIONS AND ANALYSIS

7.1 Derived Variables

7.1.1 Demographics

Age collected in CRF will be used on tables.

BMI (kg/m^2) is calculated using the following formula:

$$\text{BMI} = \text{Weight} (\text{kg}) / \text{Height}^2 (\text{m}^2)$$

7.1.2 Immunogenicity

Values below the HI antibody responses below the lower limit of quantification (Below limit of Quantification (BLQ)<10, recorded as “< 10”) will be attributed a value of 5. Values below MN antibody responses below the lower limit of quantification (Below limit of Quantification (BLQ)<14.1, recorded as “< 14.1”) will be attributed a value of 7.1. All BLQ responses for the SRH antibody (recorded as 4 mm^2) will be attributed a value of 2 mm^2 .

For HI assay:

Seroconversion rate is defined as the proportion of subjects in a given treatment group with either a ≥ 4 -fold increase in reciprocal HI titers between Day 0 and Day 21 or a rise of undetectable HI titer (i.e. < 10) pre-vaccination (Day 0) to an HI titer of ≥ 40 on Day 21.

Seroprotected rate is defined as the proportion of subjects in a given treatment group attaining a reciprocal HI titer of ≥ 40 on Day 21 (the percentage of vaccine recipients with a serum HI titer of at least 1:40 following vaccination).

For MN assay:

Seroconversion rate is defined as the proportion of subjects in a given treatment group with either a ≥ 4 -fold increase in reciprocal MN titers between Day 0 and Day 21 or a rise of undetectable MN titer (i.e. <14.1) pre-vaccination (Day 0) to an MN titer of ≥ 56.4 on Day 21.

For SRH assay:

Seroconversion rate is defined as the proportion of subjects in a given treatment group showing at least 50 % increase in GMA between Days 0 and 21.

Seroprotected rate is defined as the proportion of subjects in a given treatment group attaining an area $\geq 25 \text{ mm}^2$ following vaccination (Day 21).

GMT calculation

The GMT calculations are performed by taking the anti-log of the mean of the log titer transformations. The back-transformation for mean GMT will be calculated with two-sided, 95% confidence limits, based on the ANOVA model.

GMFR calculation

The GMFR will be derived by using Analysis of Covariance (ANCOVA) to model the difference in the log of the titer values between Day 21 and Day 0, with treatment group as main effect and baseline titer as covariate. The GMFR will be compared between the treatment groups. Pair-wise comparisons between the treatments groups will be performed using two-sided, 95% confidence, based on the least-squares mean differences from the ANCOVA model.

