#### **10.4.2 Immunogenicity Endpoints**

##### **10.4.2.1 Secondary Endpoints**

- HI antibody response induced by the Quadrivalent VLP Influenza Vaccine against the homologous and heterologous influenza strains on Days 0 and 21 in a subset of 400 subjects. HI antibody titers will be analyzed as follows:
  - GMTs of HI antibody on Days 0 and 21;
  - SC rate: the proportion of subjects in a given treatment group with either a  $\geq 4$ -fold increase in reciprocal HI titers between Day 0 and Day 21 or a rise of undetectable HI titer (i.e.  $< 10$ ) pre-vaccination (Day 0) to an HI titer of  $\geq 40$  on Day 21;
  - SP rate: the proportion of subjects in a given treatment group attaining a reciprocal HI titer of  $\geq 40$  on Day 21 (the percentage of vaccine recipients with a serum HI titer of at least 1:40 following vaccination);
  - GMFR: the geometric mean of the ratio of GMTs (Day 21/Day 0).

The immunogenicity endpoints for all four homologous influenza antigens will be evaluated according to the CBER criteria.

- MN antibody response induced by the Quadrivalent VLP Influenza Vaccine against the homologous influenza strains on Days 0 and 21, in the subset of 400 subjects, will be analysed as follows:

- GMTs of MN antibody on Days 0 and 21;
- SC rate on Day 21 (as defined above for HI);
- GMFR (Day 21/Day 0).
- SRH antibody response induced by the Quadrivalent VLP Influenza Vaccine against the homologous strains on Days 0 and 21 in a subset of 400 subjects, will be analysed as follows:
  - GMAs of SRH antibody on Days 0 and 21;
  - SC rate: proportion of subjects in a given treatment group showing at least 50 % increase in GMA between Days 0 and 21;
  - SP rate: the proportion of subjects in a given treatment group attaining an area diameter  $\geq 25 \text{ mm}^2$  following vaccination (Day 21);
  - GMFR: the geometric mean of the ratio of GMAs (Day 21/Day 0).

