4.3 Immunogenicity endpoints (subset of subjects)

4.3.1 Secondary endpoints

- HI antibody response induced by the Quadrivalent VLP Influenza Vaccine against the homologous and heterologous influenza strains on Days 0 and 21 in a subset of 400 subjects (300 who received the VLP vaccine and 100 who received the placebo). HI antibody titers will be analyzed as follows:
 - Geometric Mean Titers (GMT) of HI antibody on Days 0 and 21;
 - Seroconversion (SC) rate: the proportion of subjects in a given treatment group with either a ≥ 4 -fold increase in reciprocal HI titers between Day 0 and Day 21 or a rise of undetectable HI titer (i.e. < 10) pre-vaccination (Day 0) to an HI titer of ≥ 40 on Day 21;
 - Seroprotection (SP) rate: the proportion of subjects in a given treatment group attaining a reciprocal HI titer of ≥ 40 on Day 21 (the percentage of vaccine recipients with a serum HI titer of at least 1:40 following vaccination);
 - Geometric Mean Fold Rise (GMFR): the geometric mean of the ratio of GMTs (Day 21/Day 0).
- MN antibody response induced by the Quadrivalent VLP Influenza Vaccine against the homologous influenza strains on Days 0 and 21, in the subset of 400 subjects, will be analysed as follows:
 - GMTs of MN antibody on Days 0 and 21;
 - SC rate: the proportion of subjects in a given treatment group with either a ≥ 4 -fold increase in reciprocal MN titers between Day 0 and Day 21 or a rise of undetectable MN titer (i.e. < 14.1) pre-vaccination (Day 0) to an MN titer of ≥ 56.4 at Day 21 post-vaccination ;GMFR (Day 21/Day 0).

Note: A number of studies show the MN assay to have a two-fold or higher sensitivity than the HI assay. However, there is still limited data available on the comparative

sensitivities of these two assays and the data that is available and is largely focused on H1N1 and H3N2. As a result, since this is a secondary analysis with a relatively small sample size, a conservative approach was taken by using the HI assay correlates of protection for the MN assay.

- SRH antibody response induced by the Quadrivalent VLP Influenza Vaccine against the homologous strains on Days 0 and 21 in a subset of 400 subjects will be analysed as follows:
 - Geometric Mean Areas (GMA) of SRH antibody on Days 0 and 21;
 - SC rate: proportion of subjects in a given treatment group showing at least 50 % increase in GMA between Days 0 and 21;

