8.7.2 Analysis of Secondary Endpoints

The secondary immunogenicity endpoints are defined in section 4.3.1.

HI antibody titers will be analyzed and evaluated according to the CBER criteria, using a stepwise closed testing procedure as follows:

- GMTs of HI antibody: The point estimates and the corresponding two sided 95% CI by treatment group and strain will be calculated as the antilog of the mean and 95% CI of log transformed titer values on Days 0 and 21;
- SC rate: The point estimates and the corresponding two-sided 95% CI for subjects achieving SC by treatment group and strain will be calculated to determine whether the lower bound of the CI will meet or exceed 40%;
- SP rate: The point estimates and the corresponding two-sided 95% CI for subjects achieving SP by treatment group and strain will be calculated to determine whether the lower bound of the CI will meet or exceed 70%.
- GMFR: the geometric mean of the ratio of GMTs (Day 21/Day 0).

For SC and SP rates, the following stepwise closed testing procedure will be applied while evaluating the results against the CBER criteria (for SC rate, the lower bound of the 95% CI will meet or exceed 40%; for SP rate, the lower bound of the 95% CI will meet or

exceed 70%). The stepwise closed testing procedure will be continued until the first rejection of the CBER criteria occurs.

Step (1) A/H1N1:SC rate → SP rate → Step (2) A/H3H2:SC rate → SP rate → Step (3) B/Brisbane:SC rate → SP rate → Step (4) B/Phuket:SC rate → SP rate

MN antibody response against the homologous influenza strains on Days 0 and 21 will be analysed as follows:

- GMTs of MN antibody on Days 0 and 21 (as defined above for HI);
- SC rate: the proportion of subjects in a given treatment group with either a ≥ 4 -fold increase in reciprocal MN titers between Day 0 and Day 21 or a rise of undetectable MN titer (i.e. < 14.1) pre-vaccination (Day 0) to an MN titer of ≥ 56.4 at Day 21 post-vaccination. GMFR: the geometric mean of the ratio of GMTs (Day 21/Day 0).

SRH antibody response against the homologous influenza strains will be analysed as follows:

- GMAs of SRH antibody on Days 0 and 21;
- SC rate: proportion of subjects in a given treatment group showing at least 50% increase in GMA between Days 0 and 21;
- SP rate: the proportion of subjects in a given treatment group attaining an area ≥ 25 mm² following vaccination (Day 21);
- GMFR: the geometric mean of the ratio of GMAs (Day 21/Day 0).

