The GMFR will be derived by using ANCOVA to model the difference in the log of the titer values between Day 21 and Day 0, with treatment group as main effect and baseline titer as covariate.

The GMTs, GMFRs, SP and SC rates of the HI and MN antibody assay and the GMAs, GMFRs, SC rates, and SP rates for the SRH antibody assay will be compared between the treatment groups using descriptive statistics and 95% CI. For SC rate and SP rate, Fisher's exact tests will be used. GMT for HI, MN and GMA for SRH will be compared between treatment groups using analysis of variance (ANOVA) model. GMFR for HI, MN and SRH will be compared using analysis of covariance (ANCOVA) model.

A sub-analyses stratified by age group for the secondary immunogenicity endpoints will be performed. The analyses of the secondary immunogenicity endpoints will be repeated for the FAS.

An individual listing will be provided to include all assay results (HI, MN and SRH) and whether a particular subject has seroconverted/seroprotected based on IPP set.

In addition, the below listed figures will be generated:

- Reverse Cumulative Distribution Curves (RCDC) for Homologous Strains Measured and Heterologous Strains Measured by HI based on IPP.
- RCDC for Homologous Strains Measured by HI based on FAS.
- RCDC for Homologous Strains Measured by MN based on IPP.
- RCDC for Homologous Strains Measured by SRH based on IPP.

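### For a subject below the SRH quantification limit at Day 0, the seroconversion threshold is 3 mm², under the 4 mm² limit, so any quantifiable Day 21 area counts although a 50% rise has not been shown

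*SAP*

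**What the plan says.** SAP 7.1.2 gives the rule for SRH results below the limit of quantification (BLQ): "All BLQ responses for the SRH antibody (recorded as 4 mm^2) will be attributed a value of 2" mm². The same section and SAP 4.3.1 define SRH seroconversion with a single condition: "SC rate: proportion of subjects in a given treatment group showing at least 50 % increase in GMA between Days 0 and 21". SAP 8.7.2 and protocol 10.4.2.1 repeat it. None of these places sets a minimum Day 21 area for a subject who was BLQ at Day 0.

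For the other two assays, SAP 7.1.2 does mention undetectable baselines. Besides a four-fold rise, the HI definition accepts a "rise of undetectable HI titer (i.e. < 10) pre-vaccination (Day 0) to an HI titer of ≥ 40 on Day 21", and the MN definition has a parallel clause ending "pre-vaccination (Day 0) to an MN titer of ≥ 56.4 on Day 21".

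The SRH level of 25 mm² appears only in the definition of seroprotection.

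SRH seroconversion is a secondary immunogenicity endpoint. SAP 8.7.2 compares it between arms: "For SC rate and SP rate, Fisher's exact tests will be used".

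**The concern.** The substituted value and the percentage rule interact. Half the limit, raised by 50%, is still below the limit. For a subject who is BLQ at Day 0, the condition therefore no longer tests for a 50% rise; it tests only whether the Day 21 result is quantifiable. A reading that moves across the limit through assay noise alone would be reported as seroconversion, in either arm. The more BLQ baselines a strain has, the more its SRH seroconversion rate depends on this.

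There is also a wording fault. The rule refers to an increase in GMA, which is a geometric mean over a group, where a subject's own area must be meant.

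**Working it through.** **Inputs from SAP 7.1.2.** BLQ is recorded as 4 mm² and analysed as 2 mm². Seroconversion requires a ratio of at least 1.5. I read 4 mm² as the quantification limit.

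**The plan's substituted values.** All three are half the limit:
- SRH: 4/2 = 2.
- HI: 10/2 = 5.
- MN: 14.1/2 = 7.05, stated as 7.1.

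**Threshold from a BLQ baseline.**
- SRH: 1.5 × 2 = 3 mm², below 4 mm².
- Smallest quantifiable area: 4/2 = 2.0, a 100% increase, so it counts.
- BLQ on both days: 2/2 = 1.0, so it does not count.
- In general, half-limit substitution gives 1.5 × L/2 = 0.75 L, which is below any limit L. To bring the threshold above 4 mm², the substitute would have to exceed 4/1.5 = 2.67 mm².
- If HI and MN fold rises also use the substituted values, their thresholds are 4 × 5 = 20 and 4 × 7.1 = 28.4. Both lie above the assay limits of 10 and 14.1. Only SRH has a threshold below its own limit.

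**What a BLQ Day 0 can show.** The Day 0 area is known only to be under 4 mm². A Day 21 area of 6 mm² or more is at least 1.5 times any such value, so the measured rise is at least 50%. Between 4 and 6 mm² it is undetermined. For example, a Day 0 area of 3.9 mm² and a Day 21 area of 4.5 mm² give 4.5/3.9 = 1.15, a 15% rise, yet the plan computes 4.5/2 = 2.25 and counts it.

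**Size, under assumptions.** The documents give no SRH distribution, BLQ share or assay variability. The simulation used 2,000,000 subjects per scenario, with log-normal Day 0 areas of median 12, 6 or 4 mm² and ln SD 0.9 (about 11%, 33% or 50% BLQ). Noise per measurement had ln SD 0.10, 0.15 or 0.25.

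No true change, share of BLQ-baseline subjects classed as seroconverted:

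| Rule when Day 0 is BLQ | Noise 0.10–0.15 | Noise 0.25 |
|---|---|---|
| As written (3 mm²) | 5–16% | 12–25% |
| Day 21 ≥6 mm² | 0–0.5% | 2–5% |
| Day 21 ≥25 mm² | about 0% | about 0% |

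Over the whole arm, with 33% BLQ and noise 0.15, the no-effect seroconversion rate is 5.0% as written, 1.7% with the 6 mm² rule and 1.6% with the 25 mm² rule.

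True median rise two-fold (response ln SD 0.6, noise 0.15), whole-arm rate:

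| BLQ at Day 0 | As written | ≥25 mm² if BLQ |
|---|---|---|
| 11% | 67% | 60% |
| 33% | 64% | 45% |
| 50% | 59% | 34% |

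With 33% BLQ the 6 mm² rule gives 57%. Across the three BLQ shares it lowers the rate by about 2–10 points. The share with a true rise of at least 50% in this model is Φ[(ln 2 − ln 1.5)/0.6] = Φ(0.479) = 68.4%.

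**The case against.** The strongest objection concerns direction and reach, and most of it stands.

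- A reader might infer from the second table that the plan overstates vaccine-arm seroconversion by 7–25 points. It does not show that. Those are distances from a 25 mm² floor. The true share in the same model is 68.4%, so the written rule is at or slightly below the truth. About 85–92% of the subjects whom a 25 mm² floor removes have a genuine rise of 50% or more.
- A reader might take the HI and MN clauses as floors that SRH lacks. They are alternatives joined by *or*, so they add converters rather than restrict them. What sets SRH apart is only that its threshold lies below its own limit.
- A reader might treat 25 mm² as the natural requirement. No section links it to seroconversion, and protocol 1.3.2.1 says that MN and SRH have no available correlate of protection. For BLQ baselines it would also make seroconversion the same as seroprotection, which is reported separately.
- With no effect, misclassification is expected equally in both arms, so the Fisher comparison is not biased under the null.
- SRH seroconversion has no success criterion. Seroprotection, the baseline-adjusted GMFR, the reverse cumulative curves and the listings would show weak responses.
- The GMA wording is editorial, since the rule already speaks of a proportion of subjects.

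The objection leaves the arithmetic untouched: the rule labels subjects as having risen by 50% on data that cannot establish it.

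**Conclusion.** The point holds in a limited form. That the threshold is 3 mm² against a 4 mm² limit follows from the SAP text alone. Counting Day 21 areas between 4 and 6 mm² as seroconversion from a BLQ baseline is unsupported.

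The firm harm is false seroconversion without a true change: 5–25% of BLQ-baseline subjects under the assumed distributions and noise. The actual figure cannot be computed from the documents, because it depends on a BLQ share, spread and assay noise that they do not give. No claim that the vaccine-arm rate is overstated is justified.

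The effect is confined to the SRH seroconversion rate in the 400-subject subset. Primary vaccine efficacy, the HI-based CBER criteria and SRH seroprotection are unaffected. It is a small defect, but cheap to correct.

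**What to change.** In SAP 4.3.1, 7.1.2 and 8.7.2, and in protocol 10.4.2.1, define SRH seroconversion on the subject's own SRH area instead of GMA:

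- Day 0 quantifiable: at least a 50% increase in that subject's area.
- Day 0 BLQ: apply the 50% rule to the 4 mm² limit, so the Day 21 area must be at least 1.5 × 4 = 6 mm².
- Sensitivity analysis: when Day 0 is BLQ, require a Day 21 area of at least 25 mm², the SAP's SRH seroprotection level.
- Use the 2 mm² substitution only for GMA and GMFR.

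It would also help to report SRH seroconversion by whether Day 0 was BLQ. The rule should be fixed before unblinding; protocol section 12 already requires the SAP to be final before database lock.

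The cost is wording and one line of derivation code, with no new data. The downside is a lower reported SRH seroconversion rate, by about 2–10 points in the two-fold-rise scenarios. Some subjects who truly rose from a BLQ baseline will not be counted; in those scenarios they are the majority of the subjects dropped. That is the price of counting only rises that the measurements can show.

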5 SAMPLE SIZE AND POWER

The sample size of approximately 10,000 subjects (5,000 subjects per treatment group) was selected based on the assumption that the Quadrivalent VLP Influenza Vaccine would have a VE of at least 70% and that the attack rate in unvaccinated subjects (ARU) would be 2% or greater for laboratory-confirmed influenza cases caused by vaccine-matched strains. The sample size was chosen to have 90% power to determine whether the lower bound (LB) of the two-sided 95% CI for the primary endpoint would be greater than 40%, assuming a 10% attrition rate.

If the ARU is lower than 2%, but greater than or equal to 1.5%, this sample size will have an 80% power to determine whether the LB of the two-sided 95% CI for the primary endpoint (VE) would be greater than 40%, assuming a 10% attrition rate.

A protocol amendment will be issued to address changes to the enrollment plan or to the study extension into another season to enrol more subjects in the event of insufficient ARU.

Table 3 shows the sample size simulations result. The simulation was repeated 1000 times in order to calculate the power.

Table 3 Sample Size Simulation Result

Placebo Control AR (ARU)	VE (vs placebo)	LB of 95% CI	Power	Sample Size per Group
2%	70%	40%	90%	4430
1.50%	70%	40%	80%	4490

[Note] Under the assumptions of 70% vaccine efficacy (VE) and 2% influenza attack rate (Placebo), we expect a total of 116 to 130 cases of influenza (89 cases for Placebo and 27 cases for VLP in case of 4430 per group considering 10% dropout rate, 100 cases for Placebo and 30 cases for 5000 per group).

If the influenza attack rate is lower than 2%, but greater than or equal to 1.5%, we expect a minimum of 89 total cases.

Immunogenicity Subset

A sample size of 300 subjects (for the VLP vaccine group) was selected to ensure that the LBs of the 95% CI for the co-primary endpoints (SC and SP rates) for each strain meet CBER's criteria with 80% power (individual power is 97.4%).

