8.7.2.1 Multiplicity

A multiplicity adjustment was done at the time of sample size determination (N=300) as described below:

The lower bound (LB) of the 95% CI for the percentage of subjects achieving SC and SP for the four homologous antigens will be compared to CBER's criteria as co-primary endpoints where a stepwise closed testing approach will be applied for multiplicity of hypothesis tests. The stepwise closed testing procedure will be stopped as soon as the LB of 95% CI for SC or SP of one strain does not meet CBER's criteria.

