8.7.2.2.2 Exact 95% CIs

The exact 95% CIs (Clopper-Pearson method) will be used for proportion of SC and SP subjects within a group.

SAS® Code for SC and SP (Exact 95% CIs):

```
PROC FREQ data=<Data> ;
  BY ANTIGEN trtpn;
  TABLE SC/out=CNT binomial; *SC or SP
  EXACT binomial;
  ODS OUTPUT binomialprop=bin (where=(name1 in ('XL_BIN', 'XU_BIN')));
  run;
```

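### The SAP's HI seroconversion rule counts a rise from <10 to 20, so its ≥40 requirement for undetectable baselines has no effect

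*SAP*

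**What the plan says.** SAP 7.1.2 first deals with HI values below the quantification limit: a result recorded as <10 "will be attributed a value of 5". No use of that value is excluded. The section then defines HI seroconversion as either a ≥4-fold "increase in reciprocal HI titers between Day 0 and Day 21 or a rise of undetectable HI titer" (<10 on Day 0) that reaches at least 40 on Day 21. SAP 4.3.1 repeats the definition, including the separate condition for "a rise of undetectable HI titer (i.e. < 10) pre-vaccination (Day 0) to an HI titer of" at least 40. In neither place does the ≥4-fold alternative carry a minimum Day 0 titer.

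Protocol 10.4.2.1 has the same two alternatives but assigns no number to <10.

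The SC rate feeds a threshold decision. SAP 8.7.2 computes a two-sided 95% CI by strain "to determine whether the lower bound of the CI will meet or exceed 40" percent, and SAP 8.7.2.2.2 specifies exact Clopper-Pearson limits. For each strain SC is tested before seroprotection (SP), and SAP 8.7.2.1 says the procedure "will be stopped as soon as the LB of 95% CI for SC or SP of one strain" misses its criterion.

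**The concern.** By writing a separate condition for undetectable baselines, the SAP signals that such a subject must reach 40 to count. Once <10 has the numerical value 5, the fold-rise alternative applies to these subjects too and sets a lower bar of 20. The stricter clause then does nothing.

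Two things follow. The SC rate under the text as written is equal to or higher than the rate with a working floor of 40, never lower. And two competent programmers could obtain different rates from the same data, one applying the text literally and one applying the ≥40 clause to everyone with an undetectable baseline. That choice should not be left open on a rate compared with a licensure threshold at the head of a stepwise sequence.

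The fault arises in the SAP. In the protocol a fold rise from <10 has no defined value, so the ≥40 alternative can still operate.

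**Working it through.** **The rule, with <10 set to 5**

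| Day 0 | Day 21 | Fold rise | ≥4-fold alternative | <10 to ≥40 alternative | Counted |
|---|---|---|---|---|---|
| <10 (5) | 10 | 10/5 = 2 | no | no | no |
| <10 (5) | 20 | 20/5 = 4 | yes | no | yes |
| <10 (5) | 40 | 40/5 = 8 | yes | yes | yes |

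Any Day 21 titer of 40 or more from an undetectable baseline gives at least 40/5 = 8-fold, so the second alternative lies wholly inside the first. This does not depend on the dilution series. If the first alternative is restricted to Day 0 ≥10, only subjects going from <10 to a Day 21 titer of 20 to below 40 change status. On an assumed two-fold series that is the single pair <10 to 20.

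**The plan's own power figure**

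SAP 5 gives 300 vaccinees and 80% overall power ("individual power is 97.4", in percent). With four strains and two criteria each there are eight tests: 0.974^8 = 0.810, consistent with 80%. The 97.4% can therefore be read as the power of each test.

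**Passing counts at n = 300 (Clopper-Pearson, two-sided 95%)**

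- SC, lower bound at least 40%: 138/300 passes (46.0%, lower bound 40.26%); 137/300 fails (39.93%).
- SP, lower bound at least 70%: 226/300 is the smallest pass (70.05%).

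**Effect on one SC test**

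Let q be the share of vaccinees going from <10 to 20–<40. The SC rate as written is the rate with a working floor plus q. The documents do not give q; 1 to 5 points (3 to 15 of 300) is an assumption. The chance of passing is P(X ≥ 138), with X binomial (300, p):

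- Rate with working floor 40% (the criterion itself): p = 0.40 gives 2.0%. For q = 1, 2, 3, 4 and 5 points (p = 0.41 to 0.45) it becomes 4.5%, 9.0%, 16.1%, 26.1% and 38.5%.
- Rate 48% (assumed middle value): 77.4% becomes 86.4% (q = 1) or 92.6% (q = 2).
- Rate implied by the plan: solving P(X ≥ 138) = 0.974 gives p = 0.514. The 97.4% becomes 98.9% (q = 1) or 99.6% (q = 2).

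In observed counts, a bare pass of 138 that includes 3, 6 or 15 such subjects falls to 135, 132 or 123 with a working floor. The lower bounds are then 39.3%, 38.3% and 35.4%, all failures.

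**Upper limit on q**

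These subjects are below 40 on Day 21. If the strain also passes SP, at most 300 − 226 = 74 vaccinees are below 40, so the observed q cannot exceed 74/300 = 24.7%.

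**The case against.** The best reply is that the intent is clear. A reader who gives every clause effect would apply the ≥40 condition to undetectable baselines and the fold rise to detectable ones. Three features support this. SAP 9 declares no change from the protocol's methods, and in the protocol the floor can operate. The floor of 40 is four times the limit of 10. The SC code in SAP 8.7.2.2.2 takes a ready-made flag, so the SAP never shows that flag being computed from 5. This is fair evidence of what was meant, but none of it puts a baseline restriction into the definition, and the value 5 is assigned without limit in the section that goes on to define SC.

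A second point stands as a caution. The 2.0% to 38.5% series treats the floor-based rate as the quantity of interest. Under the rule as written, the true rates in those scenarios are 41% to 45%, above the criterion. The series therefore measures the gap between two definitions; it is not a false-positive rate under the written one.

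The consequence is also limited. A subject who reaches only 20 still fails SP, so SC can change a strain's overall result only when SP passes and the SC rate is near its threshold. The endpoint is secondary and confined to the immunogenicity subset.

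MN lies outside this point. With <14.1 set to 7.1, a rise to 28.2 is 28.2/7.1 = 3.97-fold and is not counted.

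**Conclusion.** The concern holds. As written, the HI rule counts <10 to 20 and its ≥40 clause is inert; this follows from the SAP's text and arithmetic alone. The SC rate is raised by exactly q, which is unknown and may be zero. The effect on passing an SC test is material near the 40% criterion and small at the rate implied by the planned power (97.4% to 98.9% for one point). The sizes rest on 300 evaluable vaccinees, an assumed q of 1 to 5 points and, for the 51.4% rate, on 97.4% being the power of each SC test. SP and the primary vaccine efficacy analysis are untouched. This should be corrected, but it does not threaten the trial's main conclusion.

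**What to change.** In SAP 4.3.1 and 7.1.2, define HI seroconversion as: Day 0 titer ≥10 with a ≥4-fold rise to Day 21, or Day 0 titer <10 with a Day 21 titer ≥40. Settle this before unblinding so that the derivation is not chosen with results in view.

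The cost is one sentence in two sections and no new data. The downside is that HI SC rates may be slightly lower. The protocol wording is not at fault and need not change; altering it would require a formal amendment under protocol 17.1.
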